7.2.2 Statistical Analysis Methods for Primary Outcome

Because the most intensive intervention period is during the initial 3-4 months, the primary outcome is measured at 180 days (6 months) to capture the main intervention effect. Given the primary outcome is the number of days of risky opioid use within the first 180 days following the baseline assessment collected with HLM, a mixed effects negative binomial model with a log link will be fit to estimate the difference in means between treatment and control groups. Fixed effects include treatment effect, site effect, and the baseline value of the response variable (days of use within 30 days prior to the baseline assessment timepoint), which may improve precision. Random PCP intercepts are to account for within-PCP correlation of participant response values. Since randomization was at PCP team level where PCPs practiced in teams and shared patients regularly, PCP cluster was specified as PCP/PCP team which was the unit of randomization, that is, if two or more PCPs are randomized as a single cluster, they will be analyzed as a single cluster. Letting Y_{jk} denote the response variable of a participant in site j with PCP k , treatment denotes a binary treatment indicator variable, site denotes a multi-level categorical variable representing study sites, and baseline denote the baseline value, the formula for the log-transformed expectation of Y_{jk} is given:

$$\log[E(Y_{jk})] = \beta_0 + \beta_1 \cdot \text{treatment} + \beta_2 \cdot \text{baseline} + \beta_3 \cdot \text{site} + \gamma_k,$$

where γ_k is normally distributed with mean zero and standard deviation σ_γ representing random effect by within-PCP correlation of participant responses. The negative binomial model allows for potential overdispersion of the response variable, so is more flexible than a Poisson distribution which would require the mean to be equal to the variance.

The primary hypothesis will be evaluated by testing whether the treatment effect, β_1 , is different from zero. This is equivalent to testing whether the control mean is different from the intervention mean.

The template SAS code for the primary analysis is:

```
PROC GLIMMIX DATA=dat METHOD=quad;
  CLASS PCP treat site;
  MODEL daysin180 = treat site baseline / solution DIST=negbin LINK=log ddfm=bw;
  RANDOM intercept / SUBJECT= PCP;
RUN;
```

Where:

“dat” is the name of the dataset with one row per patient participant,

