“daysin180” is the name of the primary outcome, a continuous variable indicating the number of days of risky opioid use within the first 180 days following the baseline assessment,

“treat” is a binary indicator variable coded as “1” for intervention arm STOP and “0” for control arm EUC,

“baseline” is a continuous variable indicating the number of days of risky opioid use during past 30 days prior to baseline assessment,

“site” is a categorical variable for 5 participating sites, and

“PCP” is a character variable representing PCP clusters.

The option method = quad indicates that the likelihood will be evaluated using the Gaussian quadrature method. Assessment of model fit will be reported based on standard goodness-of-fit metrics (e.g., deviance) and inspection of Pearson residuals.

The treatment effect of STOP from this model will be given as a rate ratio, the exponentiated estimate of the treatment effect, along with a 95% confidence interval. This can be interpreted as a ratio of the mean total number of days of risky opioid use for those enrolled to STOP versus EUC within the first 180 days post-randomization, when all other variables in the model are held constant. A risk ratio less than 1 would indicate fewer days of risky opioid use for those assigned to STOP compared to those assigned to EUC.

The primary outcome analysis will be performed on the Intent-to-Treat (ITT) Population, analyzing patient participants according to their PCP's randomization assignment regardless of potential exposure to the opposite assignment. The primary analysis will use multiple imputation to account for missingness of the primary outcome variable with details provided in Section 7.2.3.

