Fixed effects include treatment, piecewise linear function of time, interaction of treatment \times piecewise linear function of time, baseline risky opioid use and site. A random effect term for patient participants will be included to account for the correlation of repeated measures within the same patient participant and within-PCP correlation of participant responses. The autoregressive covariance structure will be used to take into account the correlation of the repeated measures of monthly risky opioid use. This structure specifies that observations that are more proximate to one another are more correlated than those that are more distant.

The following is an example of a model with piecewise linear functions at the breaking point of month 6 to allow the slopes that represent the change in the outcome over time to vary between Months 1-6 and Months 7-12.

The SAS code to create a linear spline variable to specify time spline “timespl” equal to “0” when time is from Months 1 to Month 6, or equal to “time – 6” when the time is greater than Month 6 is as follows.

```
DATA datmonthly;
  SET datmonthly;
  Chgpoint=6;
  If time <= Chgpoint then timespl=0;
  else if time >Chgpoint then timespl = time - 6;
RUN;
```

The model investigates whether there is treatment effect on change of monthly risky opioid use over 12 months. The estimates of time and piecewise linear time spline will provide information on the change of risky opioid use before and after Month 6. The interaction terms of treatment with time and time spline assess the difference in change of opioid use associated with the treatment effect during the two time segments. The “Estimate” statement is used to derive the following estimates and corresponding p-values:

1. Difference of time slopes in change of risky opioid use during Months 1-6 between the two treatment groups
2. Difference of time slopes in change of risky opioid use during Months 7-12 between the two treatment groups.

```
PROC GLIMMIX DATA=datmonthly METHOD=quad;
  CLASS PATID PCP time treat site;
  MODEL daysmonthly = treat time timespl treat*time treat*timespl site baseline / solution
  DIST=negbin LINK=log ddfm=bw;
  RANDOM intercept / SUBJECT= PCP;
  REPEATED / SUBJECT=PATID TYPE=AR(1);
  Estimate "Difference of change Months 1-6"
  time 0 timespl 0 treat*time 1 -1 treat*timespl 0 0/ CL ilink;
  Estimate "Difference of change Months 7-12"
  time 0 timespl 0 treat*time 1 -1 treat*timespl 1 -1/ CL ilink;
```

RUN:

where

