Another supportive analyses will explore temporal patterns of number of days of risky opioid use during the past 3 months. The 3-month (days of use in the first 90 days post-baseline) and 6-month (days of use in days 91-180 post-baseline) outcome measures will assess early intervention effects. The measures at 9 and 12 months (days of use in days 181-270 post-baseline and in days 271-360 post-baseline, respectively) will assess the durability of intervention effects (which may be maintained, increased, or decreased) over time. These data analyses will utilize a longitudinal mixed effect negative binomial regression model treating quarterly risky opioid use during months 1-3, months 4-6, months 7-9 and months 10-12 as the dependent count variables. Fixed effects include treatment, time indicator in terms of duration of past 3 months, site and an interaction between treatment and time indicator. Time indicator will enter the model as a categorical variable (1 for months 1-3; 2 for months 4-6; 3 for months 7-9 and 4 for months 10-12) to allow greater flexibility. A random effect term for patient participants will be included to account for correlation of repeated measures on the same patient participant and within-PCP

correlation of participant responses. The template SAS code to fit the model in estimating treatment effect of STOP during Months 1-3 is given below.

```
PROC GLIMMIX DATA=datquar METHOD=quad;
  CLASS PATID PCP time treat site;
  MODEL daysquar = treat|time site baseline / solution DIST=negbin LINK=log ddfm=bw;
  RANDOM intercept / SUBJECT= PCP;
  REPEATED intercept/ SUBJECT=PATID TYPE=AR(1);
  Estimate "Treatment effect during Months 1-3" treat 1 -1 treat*time 1 0 0 0 -1 0 0 0/ CL
  ilnik;
  Contrast "Treatment effect during Months 1-3" treat 1 -1 treat*time 1 0 0 0 -1 0 0 0/ CL
  ilnik;
RUN;
```

where

“datquar” is the name of the dataset with one row for each quarterly risky opioid use for each patient participant,

“daysquar” is the name of the outcome, a continuous variable indicating quarterly use of risky opioid use (days),

“treat” is a binary indicator variable coded as “1” for intervention arm STOP and “0” for control arm EUC,

“time” is a categorical variable to indicate the time of past 3 months,

“baseline” is a continuous variable indicating the number of days of risky opioid use during past 30 days prior to baseline assessment,

“site” is a categorical variable for 5 participating sites,

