“PATID” is a character variable representing patient participant ID, and

“PCP” is a character variable representing PCP clusters.

The treatment effect of STOP from this model will be presented as a rate ratio given the treatment effect and interaction of treatment x time along with a 95% confidence interval. The STOP intervention’s ability to reduce risky opioid use during months 1-3 compared to EUC is assessed by the treatment effect and interaction of treatment x time of the duration of months 1-3. The rate ratio, 95% confidence interval, and p-value will be reported for the treatment effect during months 1-3. Similarly, treatment effects of durations of months 4-6, months 7-9 and month 10-12 are obtained from the same mixed effect model.

To assess the number of days of risky opioid use during the past 180 days measured at 12 months, the data will be analyzed with a longitudinal mixed effect negative binomial regression model treating days of risky opioid use during months 1-6 and months 7-12 as the dependent count variable. The model for past 180 days is similar to the one for past 90 days specifying time indicator as a categorical variable (1 for months 1-6, and 2 for months 7-12). The STOP intervention’s ability to reduce risky opioid use during months 7-12 compared to EUC is assessed by the treatment effect and interaction of treatment x time of the duration of months 7-12.

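### Under SAS defaults the template code gives the treatment ratio as EUC/STOP, the reciprocal of the STOP-versus-EUC rate ratio that the SAP defines

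*SAP*

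**What the plan says.** **Stated direction.** SAP 7.2.2 writes the primary model with β1 multiplying a binary treatment term and reports the exponentiated effect as STOP relative to EUC. Its reading rule is "A risk ratio less than 1 would indicate fewer days of risky opioid use for those assigned to STOP". The footnotes to Tables 32-35 and 40 repeat the STOP-versus-EUC definition. For the quarterly model, SAP 7.6 says "The treatment effect of STOP from this model will be presented as a rate ratio" and judges the intervention by its "ability to reduce risky opioid use during months 1-3 compared to EUC".

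**Coded direction.** In both sections `treat` "is a binary indicator variable coded as “1” for intervention arm STOP and “0” for control arm EUC". The control-based imputation step in 7.2.3 also treats level 0 as the control arm. The arm variable is categorical in every analysis template: "CLASS PCP treat site" in 7.2.2 and 7.2.3, and "CLASS PATID PCP time treat site" in both 7.6 models. None of these statements carries a REF=, ORDER= or DESCENDING option. The 7.2.3 model also requests the pairwise difference of least-squares means for `treat`. The quarterly statements in 7.6 use "treat 1 -1 treat*time 1 0 0 0 -1 0 0 0/ CL". The first monthly one uses "time 0 timespl 0 treat*time 1 -1 treat*timespl 0 0/ CL ilink".

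No section describes inverting the output before it is reported. For the monthly model, 7.6 takes the reported ratio from the combination written in the ESTIMATE statement, so the signs there are part of the specification.

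**The concern.** The text and the code define opposite ratios. A programmer who runs the template and an author who applies the reading rule of 7.2.2 would together describe a benefit of STOP as a disadvantage, or the reverse. A large effect in the expected direction would probably be caught. An adjusted ratio close to 1 might not be. SAP 7.8 sends the binge alcohol, benzodiazepine, stimulant and marijuana outcomes through the same models, so the templates reach well beyond the primary table.

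**Working it through.** The documents state no figure that depends on the direction, so there is none to reproduce. The check applies the coded contrasts to means taken from the SAP.

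**Inputs.** EUC = 0 and STOP = 1 (SAP 7.2.2, 7.6). Planning means of 20 (EUC) and 14 (STOP) days per 90, or 40 and 28 per 180 (SAP 10.0, Scenario 1). Assumed SAS behaviour: levels sorted ascending, last level as reference, interaction columns in the order of the CLASS variables.

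1. **Quantity defined.** With STOP = 1, β1 = log(STOP) − log(EUC). The ratio is 28/40 = 0.70.

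2. **Primary model (7.2.2).** The sorted levels are 0, 1, so the reference is 1 = STOP. The non-zero treatment row is log(EUC) − log(STOP) = −β1. The ratio is 40/28 = 1.43. A negative binomial fit to simulated counts (4,000 per arm, means 40 and 28) agreed: 1.42 (95% CI 1.38 to 1.47) with the last level as reference, against 0.70 (0.68 to 0.73) for STOP versus EUC.

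3. **Imputed-data model (7.2.3).** The default pairwise difference is level 0 minus level 1, again EUC minus STOP.

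4. **Quarterly model (7.6).** Two column orders were tried for the interaction.
   - *Arm first, then quarter (apparently intended).* The coefficients fall on EUC and STOP at months 1-3. The function is estimable and equals log 20 − log 14 = 0.357, with exp(0.357) = 1.43. Reversing all signs gives 14/20 = 0.70.
   - *Quarter first, then arm (the order in CLASS).* The first and fifth coefficients fall on EUC in quarter 1 and EUC in quarter 3. Estimability requires each arm's interaction coefficients to sum to its main-effect coefficient. For EUC the sum is 1 − 1 = 0 against 1; for STOP it is 0 against −1. The function is not estimable and yields no ratio.

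5. **Monthly model (7.6).** If time is continuous, the 1, −1 signs give the EUC slope minus the STOP slope. For illustration, with assumed log-scale slopes of 0 for EUC and −0.05 for STOP, the result is 0 − (−0.05) = 0.05, and exp(0.05) = 1.05, above 1 although STOP declines faster. However, `time` is in CLASS while the variable list calls it continuous. As coded, the statement is therefore not a slope difference at all.

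6. **What changes.** Replacing a contrast by its negative turns the ratio r into 1/r and the limits (a, b) into (1/b, 1/a). The two-sided p-value stays the same. A ratio of 0.95 would print as 1/0.95 = 1.05.

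**The case against.** The strongest reply is that the text, not the snippet, fixes the reported quantity. The code is offered as a template or example and cannot run unedited: an option is misspelled in 7.6, and in 7.2.3 the data set names do not match from one step to the next. Someone must rewrite it. Tables 32-35 and 40 print each arm's mean beside the ratio, and Table 41 gives arm summaries for the supportive outcomes, so a reversed ratio would usually contradict numbers nearby. The primary test is two-sided and does not depend on direction.

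All of this stands, and it lowers the chance that an inverted ratio reaches a report. It does not remove the contradiction. The missing reference level would survive repair of the other slips, and Tables 42-45 show ratios without arm means.

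Three stronger readings are tempting and unsupported:

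- *Every table from 32 to 45 contradicts its own stated direction.* Tables 36-39 report interaction terms, Table 41 has no ratio, and the footnotes to Tables 42-45 state no direction. The below-1 rule appears only in 7.2.2.
- *The quarterly statement as printed yields EUC/STOP.* Its signs point that way, but with `time` before `treat` in CLASS it probably yields nothing.
- *Statistical significance would change.* It would not.

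**Conclusion.** The point holds for the direction of the coded estimates. Under SAS defaults, the primary treatment row and the least-squares-means difference on the imputed data are EUC minus STOP, so the exponentiated result is the reciprocal of the defined ratio: 1.43 in place of 0.70 at the SAP's planning means. The 7.6 statements carry the same signs, but their direction matters only after the separate coding faults are repaired. Point estimates and confidence limits invert; p-values do not.

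The conclusion rests on default SAS behaviour, which the SAP does not spell out, and on there being no unstated inversion step. The documents show no results, so they cannot say whether any table has been affected. It should be corrected because the code contradicts the stated estimand and the correction is free.

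**What to change.** Choose one of these, not both:

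- **Set the reference.** Write `CLASS ... treat(ref='0')` in every model and keep the 1, −1 signs. REF= moves EUC to the end of the level list, so the solution row, the least-squares-means difference and the contrasts all become STOP minus EUC.
- **Reverse the signs.** Leave the ordering, use `treat -1 1` with matching interaction signs, and also take the primary and least-squares-means estimates as STOP minus EUC.

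Doing both restores the wrong direction in the contrasts.

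Whichever is chosen, in the quarterly model put `treat` before `time` in CLASS or reorder the interaction coefficients to match. In the monthly model remove `time` from CLASS. Label every reported ratio STOP/EUC, including those in Tables 42-45, and check its direction against the arm means. Since SAP version 2.0 is dated 23 May 2025, apply the same check to any tables already produced.

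The cost is a few lines of code and labels. No data, sample size or test is affected.

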7.7 Definition of Secondary Outcome Measures

Measures of Patient-Level Outcomes

1. Days of substance use: Self-reported days of substance use are collected at baseline and once every 30 days. Patient participants are asked to specify the number of days of use in the past 30 days (range is 0-30 days, value=0 for substances that were not used). For

binge alcohol use, the measure defines the cutoff as 5+ drinks (for men under age 65), and 4+ drinks (for women and men age 65 and over). Measures of substance use are calculated as the sum of consecutive assessments of days of use in the past 30 days. For example, days of use in the past 90 days is calculated as the sum of three consecutive assessments of days of use in the past 30 days.

- a. H2.1. Days of binge alcohol use:
 - i. In the past 30 days, measured at baseline and monthly for 12 months.
 - ii. In the past 90 days, assessed at 3, 6, 9, and 12 months.
 - iii. In the past 180 days, assessed at 6 and 12 months.
- b. H2.2. Days of benzodiazepine use:
 - i. In the past 30 days, measured at baseline and monthly for 12 months.
 - ii. In the past 90 days, assessed at 3, 6, 9, and 12 months.
 - iii. In the past 180 days, assessed at 6 and 12 months.
- c. H2.3. Days of stimulant drug use (cocaine and amphetamine-type stimulants):
 - i. In the past 30 days, measured at baseline and monthly for 12 months.
 - ii. In the past 90 days, assessed at 3, 6, 9, and 12 months.
 - iii. In the past 180 days, assessed at 6 and 12 months.
- d. H2.4. Days of marijuana use.
 - i. In the past 30 days, measured at baseline and monthly for 12 months.
 - ii. In the past 90 days, assessed at 3, 6, 9, and 12 months.
 - iii. In the past 180 days, assessed at 6 and 12 months.
- e. H2.5. Days of other drug use (not including opioids, benzodiazepines, stimulants and marijuana).
 - i. In the past 30 days, measured at 3, 6, 9, and 12 months.
- f. H2.6. Increase in number of days of risky opioid use from baseline to follow-up at 6 and 12 months:
 - i. Days of opioid use in the past 30 days, measured at baseline and monthly for 12 months.
 - ii. Days of opioid use in the past 180 days, assessed at 6 and 12 months.
- g. H2.7. Prescription opioid misuse behaviors, among participants receiving prescribed opioids:
 - i. Days of taking prescribed opioids for symptoms other than for pain, using prescribed opioids more than prescribed, or taking pain medication belonging to someone else, measured at baseline and monthly for 12 months.
 - ii. COMM score, assessed at screening and at 6 and 12 months.
- h. Urine Drug Screens are used to verify self-reported drug use. Urine drug screens are conducted at baseline and at 6 and 12 months.
- i. For participants receiving prescribed opioids, the COMM provides an additional measure of prescription opioid misuse, collected at baseline and at 6 and 12 months.

2. Substance use disorder: Opioid use disorder is assessed at baseline and at 6 and 12 months using the modified World Mental Health Composite International Diagnostic Interview (CIDI). Drug (other than opioid) and alcohol use disorder measures are collected using the PDSQ at baseline and at 6 and 12 months. The PDSQ is used rather than the CIDI for these measures because it is brief and self-administered, which makes it more feasible for these follow-up assessments.
 - a. H2.8. Moderate-severe opioid use disorder (CIDI opioid items)
 - b. H2.9. Drug use disorder (PDSQ drug items)
 - c. H2.9. Alcohol use disorder (PDSQ alcohol items)
3. Overdose risk behaviors and events
 - a. H2.10. Overdose risk behavior and behavioral intention to reduce risk is measured at baseline and at 6 and 12 months (Overdose Risk Behavior Questionnaire)
 - b. H2.10. Episodes of non-fatal overdose are measured at baseline and at 6 and 12 months (Non-Fatal Overdose Questionnaire)
4. Pain symptoms and pain-related functioning
 - a. H2.11. Pain symptoms (severity, impact on functioning) are measured at baseline and at 3, 6, 9, and 12 months using the BPI short form (items #3-6 for pain symptoms and items #9A-9G for functioning).
5. Mental health
 - a. H2.12. Anxiety symptoms are measured at baseline and 6 and 12 months (PROMIS short form)
 - b. H2.12. Depression symptoms and suicidality are measured at baseline and at 6 and 12 months (PHQ-8 and PSS)
 - c. H2.13. Sleep quality is measured at baseline and at 6 and 12 months (PROMIS Sleep 4a)
6. Health-related quality of life and acute health care utilization
 - a. H2.14. Health-related quality of life is measured at baseline and at 6 and 12 months (SF-12)
 - b. H2.15. ED and hospital utilization is measured using participant self-report of acute care events (ED visits, hospitalizations for medical reasons, hospitalizations for detoxification), collected at baseline and at 6 and 12 months.

Measures of provider-level outcomes

Measures of provider treatment practices are collected from the EHR at baseline and 12 months, for patient participants. The data extracted for each patient participant will be for the period beginning 12 months prior to study participation, through 12 months following enrollment.

1. H3.1. Prescriptions for opioids: number of patient participants receiving prescriptions for high-dose opioids (>90 MME); moderate-dose opioids (50-90 MME); and any opioids: number of prescriptions; daily prescribed dose; and total number of days prescribed.
2. H3.2. Prescriptions for benzodiazepines: number of patient participants receiving benzodiazepine prescriptions and number receiving both chronic opioid and benzodiazepine prescriptions: number of prescriptions; daily prescribed dose, and total number of days prescribed.

3. H3.3. Prescriptions for naloxone: number of patient participants receiving at least 1 prescription.
4. H3.4. Urine Drug Screens: number ordered and completed for each patient participant.
5. H3.4. Diagnosis of OUD: number of patient participants receiving a new diagnosis of OUD during the study period.
6. H3.4. Primary care visits: number of scheduled visits per patient participant.

